5.2 Participant Inclusion Criteria

- 1. Healthy adults, aged 18-50 years on the day of screening
- 2. Willing and able to provide written informed consent
- 3. If female and of childbearingⁱ potential, willing to use a highly effective methodⁱⁱ of contraception from screening until 18 weeksⁱⁱⁱ after last injection
- 4. If male and not sterilised, willing to avoid impregnating female partners^{iv} from screening until 18 weeksⁱⁱⁱ after last injection
- 5. Willing to avoid all other vaccines from within 4 weeks before and after the first and second injection
- 6. Willing and able to comply with visit schedule, complete online diaries and provide samples
- 7. Willing to abstain from donating blood for three months after the end of their participation in the trial or longer, if necessary
- Willing to grant authorised persons access to his/her trial-related medical record and GP records either directly or indirectly
 - i A woman will be considered of childbearing potential following menarche and until becoming postmenopausal unless permanently sterile. Permanent sterilisation methods include hysterectomy, bilateral salpingectomy and bilateral oophorectomy. A post-menopausal state is defined as no menses for 18 months without an alternative medical cause.
 - ii The following methods are considered highly effective:
 - combined (estrogen and progestogen containing) hormonal contraception associated with inhibition of ovulation oral, intravaginal or transdermal;
 - progestogen-only hormonal contraception associated with inhibition of ovulation oral, injectable or implantable
 - intrauterine device (IUD);
 - intrauterine hormone-releasing system (IUS);
 - bilateral tubal occlusion;
 - vasectomised partner, where the vasectomised partner has received medical assessment of the surgical success; and
 - sexual abstinence, defined as refraining from heterosexual intercourse must be the preferred and usual lifestyle of the participant.
 - iii Nonclinical studies of saRNAs [37] showed maximal expression of the vaccine immunogen at 7 days post-immunisation, approaching baseline by 3 weeks post-immunisation, with some residual very low expression seen out to 9 weeks. Biodistribution studies with LNP-MARVsaRNA, LNP-EBOVsaRNA and LNP-LASSAsaRNA are planned, but in the absence of data we wish to take a conservative approach to the contraception period and require an 18-week washout period.

iv Through the use of condoms or sexual abstinence (see definition in footnote ii above)

It is recommended that participants have an up to date vaccination status for any required immunisations.

5.3 Participant Exclusion Criteria

- 1. Pregnant or lactating
- 2. Has a significant clinical history, physical finding on clinical examination during screening, or presence of a disease that is active or requires treatment to control it, including cardiac, respiratory, endocrine, metabolic, autoimmune, liver, neurological, oncological, psychiatric, immunosuppresive/immunodeficient or other disorders which in the opinion of the investigator is not compatible with healthy status, may compromise the volunteer's safety, preclude vaccination or compromise interpretation of the immune response to vaccine. Individuals with mild/moderate, well-controlled comorbidities are allowed.
- 3. History of Marburg virus, Ebola virus and/or Lassa virus infection
- 4. History of anaphylaxis or angioedema
- 5. History of severe or multiple allergies to drugs or pharmaceutical agents
- 6. History of severe local or general reaction to vaccination defined as:
 - a. **local**: extensive, indurated redness and swelling involving most of the arm, not resolving within 72 hours
 - b. **general**: fever ≥39.5 °C within 48 hours; bronchospasm; laryngeal oedema; collapse; convulsions or encephalopathy within 72 hours
- 7. Ever received an experimental or authorised vaccine against Ebola, Marburg, or Lassa fever viruses
- 8. Receipt of any immunosuppressive agents within 18 weeks of screening by any route other than topical
- 9. Detection of antibodies to hepatitis C
- 10. Detection of antibodies to HIV
- 11. ALT/AST exceeding the upper limits of normal ≤1.0
- 12. Abnormal urine analysis result (3 x repeats >24 hours apart are allowed)
- 13. History or current diagnosis of myocarditis, pericarditis, or other significant inflammatory heart disease, or unexplained chest pain, palpitations or dyspnoea with ECG changes at screening. Grade 1 and above abnormalities in routine laboratory parameters (see Table 4) using the FDA toxicity table Toxicity Grading Scale for Healthy Adult and Adolescent Volunteers Enrolled in Preventive Vaccine Clinical Trials, taking account of local laboratory reference ranges. https://www.fda.gov/media/73679/download
- 14. Participating in another clinical trial with an investigational drug or device or treated with an investigational drug within 28 days of screening.

15. Has received an immunisation within 28 days of screening

5.4 Withdrawal criteria

Participants are free to withdraw from the trial at any time without giving a reason. Those who withdraw will be encouraged to attend a final visit, primarily for safety reasons.

The investigator may at any time withdraw a participant if his/her participation is no longer considered safe or relevant.

The date and reason (if given) for withdrawal must be recorded in the CRF.

If a participant for any reason withdraws or is withdrawn from the trial or has a significant protocol deviation, he/she will be replaced to ensure the per-protocol targets are achieved for the primary endpoints.

In consenting to the trial, participants are consenting to trial treatment, trial follow-up and data collection.

An individual participant may stop injections early or be stopped early for any of the following reasons:

- Pregnancy in the participant
- Unacceptable toxicity that precludes further injections
- Intercurrent illness that prevents further injections including emergent conditions that meet the exclusion criteria
- Withdrawal of consent for injections by the participant

A decision by the Medical Delegate to discontinue further injections should be discussed with the local PI, and the Chief Investigator/Medical Delegate should be informed using the expedited reporting method described in **Section 8**. They may recommend additional investigations and/or referral for a specialist opinion.

As participation in the trial is entirely voluntary, a participant may choose to discontinue the trial treatment at any time without penalty or loss of benefits to which they are otherwise entitled. Although the participant is not required to give a reason for discontinuing their trial treatment, a reasonable effort should be made to establish this reason while fully respecting the participant's rights. The implications of withdrawing and how this may impact on the results and interpretation of the trial, will be explained to the participant.

Participants should remain in the trial for the purpose of follow-up and data analysis (unless they withdraw their consent from all stages of the trial, in which case refer to **Section 9.8**).

Data that are already collected from participants who stop follow-up early will be included in the analysis.

6. RANDOMISATION AND ENROLMENT PROCEDURES

6.1 Randomisation and Registration Practicalities

Investigator site staff will know the allocated dose, but participants and laboratory staff will not. Online randomisation software (Sealed Envelope) will be used at the site to randomise participants in the EML-Vac trial.

6.2 Unblinding

There will be no unblinding of the participants or laboratory staff during the course of the trial. Unblinding will only take place in an emergency situation.

In case of an emergency, the Investigator has the sole responsibility for determining if unblinding of a participant's study intervention assignment is warranted. Participant safety must always be the first consideration in making such a determination. If the Investigator decides that unblinding is warranted, the Investigator may contact the Sponsor to discuss the situation prior to unblinding a participant's study intervention assignment unless this could delay emergency treatment for the participant. If a participant's study intervention assignment is unblinded, the Sponsor must be notified within 24 hours of this occurrence. The date and reason for the unblinding must be recorded.

The trial EDC system will include an automated unblinding facility, in case unblinding is required. In the event that emergency unblinding of an individual participant is required, authorised staff (as documented on the delegation log) will follow trial procedures to unblind the participant in question and proceed with expedited reporting if required.

6.3 Co-enrolment Guidelines and Reporting

Co-enrolment in other clinical trials with an investigational or non-investigational drug or device is not permitted, and individuals who have been treated with an investigational drug within 56 days before the first vaccination will be excluded.

All other co-enrolments should be discussed with the Chief Investigator and will be decided on a case-by-case basis.

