2.1 Trial Schema

TABLE 1: TRIAL GROUPS

Group	Description	Active Dose (µg) Prime & boost	Interval between doses	Age (years)	N
Group 1	LNP-MARVsaRNA-01, plus two buffered saline placebo	5 μg	12 weeks	18-50	8
Group 2	LNP-EBOVsaRNA-01, plus two buffered saline placebo	4 μg	12 weeks	18-50	8
Group 3	LNP-LASSAsaRNA-01, plus two buffered saline placebo	4 μg	12 weeks	18-50	8
Group 4	LNP-MARVsaRNA-01, LNP-EBOVsaRNA-01, plus one buffered saline placebo	MARV 5 μg plus EBOV 4 μg (9 μg in total)	12 weeks	18-50	8
Group 5	LNP-MARVsaRNA-01, LNP-EBOVsaRNA-01, LNP-LASSAsaRNA-01	MARV 5 μg plus EBOV 4 μg plus LASSA 4 μg (13 μg in total)	12 weeks	18-50	8
Total					

Figure 1: Trial Entry

(n=40)

- 1. To evaluate the safety and immunogenicity of two immunisations with LNP-MARVsaRNA-01 administered IM 12 weeks apart at a $5 \mu g$ dose in 8 participants age 18-50 years.
- 2. To evaluate the safety and immunogenicity of two immunisations with LNP-EBOVsaRNA-01 administered IM 12 weeks apart at a 4 μ g dose in 8 participants age 18-50 years
- 3. To evaluate the safety and immunogenicity of two immunisations with LNP-LASSAsaRNA-01 administered IM 12 weeks apart at a $4 \mu g$ dose in 8 participants age 18-50 years
- 4. To evaluate the safety and immunogenicity of two immunisations with a combination of LNP-MARVsaRNA-01 (5 μ g) and LNP-EBOVsaRNA-01 (4 μ g) administered IM 12 weeks apart (total 9 μ g) in 8 participants age 18-50 years
- 5. To evaluate the safety and immunogenicity of two immunisations with a combination of LNP-MARVsaRNA-01 (5 μ g), LNP-EBOVsaRNA-01 (4 μ g) and LNP-LASSAsaRNA-01 (4 μ g) administered IM 12 weeks apart (total 13 μ g) in 8 participants age 18-50 years

TRIAL ASSESSMENT SCHEDULES

Table 2: Trial Assessment Schedule for all groups

Trial Visit	V1	V2	V2a	V3	V4	V5	V5a	V6	V7	V8	V9	V10	V11
Visit Type (site or telephone)	Site	Site	Site	Site	Site	Site	Site	Site	Site	Site	Site	Site	Site
Trial Week	-8	0	0	1	4	12	12	13	14	16	24	36	52
Trial Day	-	0	1	7	28	84	85	91	98	112	168	252	364
Windows (days)	−56 to −1	-	none	0 to +2	-2 to +2	-4 to +7	none	0 to +2	-2 to +2	-4 to +4	-7 to +7	-20 to +7	-36 to +7
Informed consent	х												
Medical history demographics	х												
Eligibility assessment	х	х											
Physical examination	Х	х		х		х		Х					
ECG	Х	х				х							
Weight/height (BMI)	Х												
Vital signs (BP, HR, O ₂ saturation and oral temperature)	х	Х	Х	Х	Х	х	Х	Х	Х	Х	х	Х	х
Concomitant medication	Х	Х	Х	х	Х	х	Х	Х	Х	Х	х	Х	х
Randomisation		Х											

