5. PARTICIPANT ENTRY

There will be **no exceptions** to eligibility requirements at the time of enrolment. Questions about eligibility criteria should be addressed prior to attempting to enrol the participant.

The eligibility criteria are the standards used to ensure that only medically appropriate participants are considered for this trial. Participants not meeting the criteria should not join the trial. For the safety of the participants, as well as to ensure that the results of this trial can be useful for making treatment decisions regarding other patients with similar health statuses, it is important that no exceptions be made to these criteria for admission to the trial.

Participants will be considered eligible for enrolment in this trial if they fulfil all the inclusion criteria and none of the exclusion criteria, as defined below.

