5.1 Pre-Randomisation Investigations

Informed consent to enter into the trial must be obtained from participants after explanation of the aims, methods, benefits and potential hazards of the trial and *before* any trial-specific procedures are performed or any blood is taken for the trial. Participants must be willing and able to provide informed consent (as detailed in Section 5.2). This therefore excludes: persons deprived of their liberty by a judicial or administrative decision, persons under psychiatric care and persons admitted to a health or social institution for purposes other than research; and persons who are the subject of a legal protection measure or who are unable to express their consent.

It must be made completely and unambiguously clear that the participant is free to refuse to participate in all or any aspect of the trial, at any time and for any reason, without incurring any penalty or affecting their treatment.

Signed consent forms must be kept by the investigator and documented on the case report form (CRF) and a copy given to the participant. With consent, the participant's GP will be sent a letter informing them of their patient's intention to participate in the trial and requesting that they corroborate their patient's medical history. Corroboration may also be obtained via the trial team accessing patient's electronic care summaries, GP and other medical records from local systems, or via participants bringing their medical care summaries from their GP to the trial team. However, participants may be enrolled based on the medical history given at the screening visit only, at the investigator's discretion.

Investigator sites registered with The Overvolunteering Protection System (TOPS) should run checks for the purposes of assessing exclusion criterion 13.

Screening procedures and investigations are listed in Table 2 and covered in more detail in Section 5.2 below.

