9.2 Procedures During the Screening Period

Screening will take place as close to the planned enrolment as possible, no longer than 8 weeks before enrolment but allowing time for all relevant laboratory assessment to check participant eligibility.

9.2.1 **INFORMED CONSENT**

Participants will be provided with information about the product, trial design and data collection in writing. They will have the opportunity to ask questions in person or on the phone.

Key points to communicate during the informed consent process:

- That we do not know if the vaccine will prevent Marburg virus, Ebola virus or Lassa virus infection
- That the vaccine does not contain any infectious component and cannot cause symptoms associated with Marburg virus, Ebola virus or Lassa virus infection
- That pregnancy is to be avoided until 18 weeks after the second injection as the safety of the vaccine is not known

If they are happy to proceed, they will be asked to indicate their informed consent in writing prior to answering questions about their health and providing samples for the screening investigations. Laboratory investigations or other screening procedures defined in this protocol that have been performed at the local clinical sites(s) for some other purpose (routine NHS visit, healthy volunteer database screening, other research) may be used for the purpose of screening so long as the date they were performed is within the window period defined in this protocol.

A copy will be provided to the participant and one copy kept in the trial file according to local procedures.

9.2.2 **ELIGIBILITY**

To assess eligibility, demographic information, a past and current medical history, and details of all current medication will be collected on worksheets and transcribed into the EDC system. Details of contraception to assess the risk of pregnancy arising in the participant/their partner will also be collected.

The screening examination will include weight (kg), height (cm), temperature, blood pressure, pulse, oxygen saturation, inspection of the skin to exclude severe eczema and respiratory, cardio-vascular, abdominal and neurological examination. An assessment of cervical, axillary and inguinal lymph nodes will also be undertaken.

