9.3 Procedures at Enrolment

9.3.1 ELIGIBILITY

Study staff will review any new medical conditions or new medications since the screening data were collected and, for female participants, any changes in contraception. Temperature, blood pressure, pulse, oxygen saturation and inspection of the skin will be repeated at the enrolment visit in case anything has changed. Study staff will repeat the other aspects of the physical examination done at the screening visit if symptoms indicate the need for this. All this information will be recorded on the EDC system.

A temperature over 37.5°C would prevent injection on the day. Clinicians should consult the PI/Medical Delegate if there are any Grade 1 (mild) symptoms or signs listed in Table 4.

Blood for immunogenicity testing will be collected. Samples will be sent to the central laboratory at Imperial College London for analysis.

For female participants of childbearing potential, a pregnancy test will be performed by analysis of a urine sample for Human Chorionic Gonadotrophin (HCG) and a negative result will be confirmed before proceeding to enrolment.

9.3.2 **ENROLMENT/RANDOMISATION**

Confirmation of eligibility will depend on entering screening data in the EDC system.

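### The exclusion list in Section 5.3 omits the 56-day investigational-drug rule of Section 6.3, so a volunteer screened on days -27 to -1 can pass the list and still be excluded

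*Protocol*

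**What the plan says.** Section 5 of the protocol makes its own lists the test of entry: volunteers are eligible "if they fulfil all the inclusion criteria and none of the exclusion criteria, as defined below", and no exceptions are allowed. Criterion 14 in Section 5.3 excludes anyone "Participating in another clinical trial with an investigational drug or device or treated with an investigational drug within 28 days of screening". It therefore has two limbs: concurrent participation, and recent treatment counted back from screening.

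Section 6.3, on co-enrolment, excludes those "treated with an investigational drug within 56 days before the first vaccination will be excluded". This interval is twice as long and is counted from a different day. No item in Section 5.2 or 5.3 repeats it.

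Table 2 allows screening (V1) from day -56 to day -1. Section 9.2 adds: "Screening will take place as close to the planned enrolment as possible, no longer than 8 weeks before enrolment". Table 2 also schedules an "Eligibility assessment" at both V1 and V2, the latter being the visit of randomisation and first vaccination.

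**The concern.** The two washout rules differ in length and in anchor, and only the one in Section 5.3 belongs to the list that settles eligibility. When screening is close to vaccination, 28 days before screening is less than 56 days before vaccination. Someone who has finished an earlier trial can then satisfy every listed criterion and be eligible under Section 5, although Section 6.3 says that person is to be excluded.

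Several steps could bring an earlier dose to light, but none says which interval to apply:

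- **Screening history.** Section 9.2.2 collects past and current medical history, but for drugs only current medication.
- **Review at enrolment.** Under Section 9.3.1 staff "review any new medical conditions or new medications since the screening data were collected". A dose given before screening is not new.
- **GP corroboration.** It is optional, since "participants may be enrolled based on the medical history given at the screening visit only" at the investigator's discretion (Section 5.1).
- **Over-volunteering check.** Section 5.1 asks for it at registered sites "for the purposes of assessing exclusion criterion 13". Criterion 13 concerns inflammatory heart disease and laboratory abnormalities; the item meant is 14.

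At stake is the reading of safety data in a first-in-human trial with 8 participants per group. Recent exposure to another investigational product can complicate the causality assessment of an adverse event.

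**Working it through.** The protocol gives no figure to reproduce; the check is day counting.

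**Inputs**

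- Criterion 14, treatment limb: 28 days back from screening (Section 5.3).
- Section 6.3: 56 days back from first vaccination.
- First vaccination: day 0 (Visit 2). Screening: day -s, with s from 1 to 56 (Table 2).
- Last investigational dose: day -d, with d at least s. The volunteer is no longer in the earlier trial; otherwise the first limb of criterion 14 excludes.

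**Rules**

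- Criterion 14 excludes if d - s ≤ 28, that is, d ≤ 28 + s.
- Section 6.3 excludes if d ≤ 56.
- A volunteer passes the list but is excluded by Section 6.3 when 28 + s < d ≤ 56. Such a d exists only for s ≤ 27.
- Number of such last-dose days: 56 - (28 + s) = 28 - s.

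**Results**

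| Screening day | Criterion 14 reaches back to | Last-dose days in the gap | Width |
|---|---|---|---|
| -1 (outer bound) | day -29 | -56 to -30 | 27 days |
| -7 | day -35 | -56 to -36 | 21 days |
| -14 | day -42 | -56 to -43 | 14 days |
| -21 | day -49 | -56 to -50 | 7 days |
| -27 | day -55 | -56 | 1 day |
| -28 | day -56 | none | 0 |

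If both rules are read strictly, so that the boundary day is not within the interval, the gap shifts by one day (days -55 to -35 for screening on day -7). The widths and the affected screening days, -27 to -1, stay the same.

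On the strict reading the shortest interval from last dose to vaccination that the list admits is 28 + s days: 35 at s = 7 (35/56 = 63%), 42 at s = 14 (75%) and 49 at s = 21 (88%). The outer bound is 29 at s = 1 (52%). The inclusive reading adds one day to each. Screening on day -1 is unlikely, because laboratory results must be available before enrolment.

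**Example.** Earlier trial finished, last dose on day -40, screening on day -7. From dose to screening: 40 - 7 = 33 days, more than 28, so criterion 14 is passed. From dose to vaccination: 40 days, less than 56, so Section 6.3 excludes.

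**Other direction.** For s = 29 to 56, criterion 14 reaches back 57 to 84 days and is the stricter rule, so the list has no gap there.

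**The case against.** The strongest reply is that the two rules do not collide. Both are exclusions, Section 6.3 is mandatory and clear, and a site that applies the whole protocol turns the volunteer away. The anchors even suggest two gates: criterion 14 at screening, and Section 6.3 at the second eligibility assessment on the day of vaccination. With one centre and 40 participants, a site working from the list alone is hypothetical. Such a site would still enforce 28 days before screening and bar anyone currently in another drug or device trial. The protocol gives no reason for 56 days, so nothing shows that 35 to 49 days would impair causality assessment.

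Much of this stands, and it limits the weight of the point. Joint application does remove the gap, and harm cannot be quantified. But the two-gate reading is stated nowhere, and Section 5 does more than forbid waivers: it declares anyone who clears its lists eligible. That statement is at odds with a further exclusion placed in a later section. The affected screening days are not a remote corner of the window either, since Section 9.2 steers screening towards enrolment, where the gap is widest.

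It is also fair to note that Section 6.3 bars co-enrolment in trials of non-investigational drugs or devices, which criterion 14 does not. That is a separate mismatch and does not weaken this one.

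**Conclusion.** The point holds. For screening on days -27 to -1, the Section 5.3 list admits volunteers whom Section 6.3 excludes, over a range of 28 - s last-dose days. The result rests on two conditions: the volunteer has left the earlier trial, and eligibility is judged from the list alone.

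The protocol gives neither the distribution of screening days nor the frequency of recent trial participation, so the number of people affected is unknown. No sample size, interval or error rate changes. It is a modest inconsistency, but it sits in an operative entry rule of a first-in-human trial and should be corrected.

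**What to change.** Keep both limbs of criterion 14 and add a third: *or has received any investigational drug in the 56 days preceding the first vaccination*. The list then carries the Section 6.3 rule for every screening day, and nothing is relaxed for volunteers screened early.

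If the sponsor prefers a single interval, state it identically in Sections 5.3 and 6.3, count it from first vaccination, keep the limb on concurrent drug or device trials, and acknowledge any loosening. A single 56-day interval would shorten the present exclusion by (28 + s) - 56 = s - 28 days for screening on days -56 to -29: 1 day at s = 29, 28 days at s = 56. Only 84 days (28 + 56) would lose nothing.

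In Section 5.1, the over-volunteering check should cite criterion 14 instead of 13.

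The cost is one clause and one corrected number. If the site already applies both sections, nothing changes; if it works from the list alone, its pool of volunteers becomes slightly smaller.
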